9.6 Data Analyses

Phase 1 Data Analysis: See Section 9.5.1

Phase 2 Data Analysis: We plan to assess 4 candidate intervention components for possible inclusion in an optimized intervention that will be evaluated in a future RCT. To do so, we will use a balanced factorial ANOVA illustrated in Table 2. Each component will have two conditions producing a $2^4 = 16$ cell design with 4 main effects, 6 possible 2-way interactions, 3 possible 3-way interactions, and 1 possible 4-way interaction. In a fully balanced design using effect coding (not dummy coding), all effects in the model are uncorrelated and the n for each condition for all effects is N/2 (i.e., 96 without attrition; 79 estimated with 17% attrition for this primary outcome). Note that specific cells are not compared against other specific cells.

We will use a general linear model with each candidate component coded using effect (1 vs -1) coding. Recruitment site, sex, age, and OAT type will be covariates. The pragmatic exigencies of field research will likely result in imperfect balance (e.g., individual cells may have slightly varying n). However, we anticipate only very small variations in cell sizes and thus estimated model coefficients will be nearly, but not perfectly, uncorrelated.

To augment traditional frequentist statistics and facilitate interpretation we will calculate the Bayes factor. Based on the observed data, a Bayes factor estimates the strength of evidence supporting one hypothesis (model) in favor of a competing hypothesis (model).³²

We will track which classes each participant attends, and who teaches each class. As a sensitivity analysis, we will include not only site as a fixed effect, but also teacher. We will include a dummy variable for each teacher to represent whether or not the participant had exposure to that particular teacher (i.e., took at least one class with that teacher).

Determination of Final Intervention Components:

Goal: To determine which components will be included in the final, optimized intervention package.

Components:

All participants: attendance at 1 class (with 2 time choices) per week; materials for personal practice

1. Personal practice videos featuring study yoga teachers
2. Initial and 1-month 1:1 session with a yoga teacher
3. Text messages cuing personal practice
4. Monetary incentives for class attendance

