Once data collection is complete, we will convene a meeting (or conference call) to make decisions about which intervention components should be included in the final intervention package. Participants in this meeting will include:

1. MPIs and co-Is and consultant [name];
2. Selected NCCIH staff (e.g., PO); and
3. Selected yoga instructors

At this meeting we will review all data collected.

Step 1: For each intervention component, we will first review the main and 2nd order interaction effects from the factorial experiment on the primary outcome of number of yoga minutes per week. We assume data will be missing at random. Missing data will be addressed using multiple imputation by chained equations.³³ Because the goal is intervention optimization, retention of components will not be based on a single criterion. We will initially choose to include all components for which there is a main or sympathetic interaction effect with a) an effect size (SMD) of 0.40 (estimated, based on preliminary data, to be 31 mins of yoga per week) or greater favoring the component; OR b) $p < .10$ favoring the component OR c) if the estimated Bayes factor provides substantial or stronger evidence preferring the intervention hypothesis to the hypothesis of no treatment effect. (See below for more information on Bayes factor).

Special cases:

1. Of monetary incentives for class attendance, we will look specifically at class attendance. If monetary incentives increase class attendance, and do not decrease overall minutes of practice, we will choose to include.
2. 3rd and 4th order interactions may be tricky to interpret. We will look at them, but place priority on main effects and 2nd order interactions in making decisions.
3. It is possible that 2nd order interactions may be antagonistic where the combination of two or more components is less effective than would be expected based on the main effects alone. At the same time, there may be significant positive main effects for both components. In this case, we will examine graphical depictions of results in order to determine whether to include both of the two components in question.

Step 2: All components that pass Step 1 will then be examined in light of their feasibility and acceptability. Data that bear on feasibility and acceptability include:

1. Participants' responses to qualitative interviews
2. Yoga instructors' experiences (field notes)

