3. Feedback from administrators/ clinicians at sites [from field notes (clinicians) and structured interviews (key administrators)]
4. Adverse events determined to be related to a given component
5. Number of 1:1 sessions attended (relevant for the 1:1 session intervention component only); use of personal practice videos (relevant for the personal practice video component only). We note that even one 1:1 session, or a small amount of use of personal practice videos, could have an impact on pain interference or other relevant outcomes.
6. % of follow-up assessments completed (not expected to be different between groups; we would consider a difference of 15% in proportion of participants observed at M3 to be of concern, and would likely be a statistically significant difference)

In determining feasibility, each component that passed Step 1 will be determined to be:

1. Acceptable and feasible without any changes.
2. There are minor changes that we judge do not affect the core nature of the intervention that we can make to increase acceptability and feasibility to a higher level (e.g., 1:1 meetings were scheduled for 45 minutes but everyone agrees that 30 minutes was adequate and even preferable).
3. Not acceptable/ feasible.

Step 3. All components that passed Step 1 and Step 2 will be included in the final optimized intervention. We will make minor changes to components if indicated in Step 2.

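### Step 3 keeps every component that passed Steps 1 and 2 without re-estimating its effect after Step 2 has removed a partner, so a component whose predicted effect in the final package is zero or negative can be retained.

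*Combined protocol and SAP*

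**What the plan says.** All the relevant text is in section 9.6, Data Analyses.

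- **Model.** "We will use a general linear model with each candidate component coded using effect (1 vs -1) coding".
- **Step 1.** "We will initially choose to include all components for which there is a main or sympathetic interaction effect", provided one of three criteria is met: "an effect size (SMD) of 0.40 (estimated, based on preliminary data, to be 31 mins of yoga per week) or greater favoring the component"; a p-value below .10 in the component's favour; or a Bayes factor giving at least substantial support.
- **Step 2.** "All components that pass Step 1 will then be examined in light of their feasibility and acceptability". Each component is classed separately, and the lowest class is "Not acceptable/ feasible".
- **Step 3.** "All components that passed Step 1 and Step 2 will be included in the final optimized intervention". The only further action is to make the minor changes identified at Step 2.

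One provision deals with dependence between components: special case 3 under Step 1. It concerns antagonistic second-order interactions between components that both have positive main effects: "In this case, we will examine graphical depictions of results in order to determine whether to include both of the two components in question". Nothing comparable covers sympathetic interactions, and nothing on interactions follows Step 2.

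**The concern.** With effect coding, a Step 1 main effect is an average over each partner being present for half the participants and absent for the other half. A sympathetic interaction is, by definition, evidence that a component does more with its partner than without it. Both are sound grounds for entry while the partner is still available. If Step 2 then removes the partner, the partner is fixed at No in the package going forward, and neither quantity describes what the survivor will add there.

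The stated objective is an efficient combination of components that maximizes yoga dosage, for testing in a later RCT. Efficiency belongs to the final combination, and no written step evaluates that combination. At stake is an element that adds cost and participant burden to the next trial without adding minutes.

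**Working it through.** **Inputs.** From section 9.2: analysable n = 158 (79 per level of each component). From Step 1: p < .10, and SMD 0.40 equated to 31 min/week. Assumption: the SD implied by that pairing, 31/0.40 = 77.5 min/week. Effects are scaled as 2b, so the interaction 2·b13 is half the difference between component 1's effects with and without component 3.

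**The plan's own figure.** With 79 per level and two-sided alpha .10, power is 0.808 at d = 0.40 and 0.933 at d = 0.50. The minimum detectable effect at 80% power is 0.396. These agree with the plan's statements of over .80 and over .90. Section 9.2 writes the error rate as alpha/2 = .10. Two-sided .10 is used here because it matches Step 1 and the stated 0.40.

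**Precision.**
- SE of any main or two-way effect: 2/√158 = 0.159 SD.
- Smallest estimate with p < .10: 1.645 × 0.159 = 0.262 SD, or about 20 min/week. An estimate of 0.40 therefore always meets the p-value criterion as well.
- SE of component 1's effect with component 3 fixed and the others averaged: √2 × 0.159 = 0.225 SD, or about 17 min/week.

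**Algebra.** Component 1's effect is 2(b1 + b13) with component 3 present and 2(b1 - b13) with it absent. Take estimates 2·b1 = 0.27 and 2·b13 = 0.27. Both exceed 0.262, so component 1 passes by either route. The predicted effect is 0.54 SD (0.54 × 77.5 ≈ 42 min/week) with component 3 and 0.27 - 0.27 = 0 without it. With 2·b1 = 0.30 and 2·b13 = 0.40, the prediction without component 3 is -0.10 SD.

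**How often the pair reaches Step 2.** Suppose component 1 adds an amount D only with component 3 present, and component 3 adds nothing alone. Both main effects and their interaction then equal D/2. Let p be the chance that one such estimate passes; the three estimates are independent in a balanced design.
- Component 1 passes: 1 - (1 - p)².
- Both pass: p + (1 - p)p². Either the interaction passes and admits both, or it fails and both main effects pass.

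At D = 0.50, p = 1 - Φ((0.262 - 0.25)/0.159) = 0.471. Component 1 passes with probability 1 - 0.529² = 0.72, and both pass with probability 0.471 + 0.529 × 0.471² = 0.59.

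| D (SD) | min/week | p | Component 1 passes | Both pass |
|---|---|---|---|---|
| 0.40 | 31 | 0.349 | 0.58 | 0.43 |
| 0.50 | 39 | 0.471 | 0.72 | 0.59 |
| 0.80 | 62 | 0.808 | 0.96 | 0.93 |

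A simulation of the 16-cell design (4,000 runs, 158 retained at random) gave 0.573 and 0.961 for component 1 passing at D = 0.40 and 0.80, in agreement.

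The last column is the relevant one. Step 2 examines only components that passed Step 1, so component 3 can be rejected there only if it passed too. The failure rate is that column multiplied by the probability that Step 2 rejects component 3, which the documents do not give and which could lie anywhere from 0 to 1.

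**What a recheck would see.** Drawing the three estimates from normal distributions at D = 0.50, the predicted effect of component 1 without component 3 is zero or negative in about 61% of the trials in which both pass. In the other 39% or so the estimate is positive, although the true effect is zero.

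These figures count only the two main effects and the interaction of the pair. They leave out the Bayes-factor route and interactions with components 2 and 4.

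**The case against.** The strongest reply is that section 9.6 describes a meeting and not an algorithm. The investigators, a consultant, funder staff and yoga instructors will review all the data, including the second-order interactions. Inclusion at Step 1 is only initial, and retention is not tied to one criterion. A group that has admitted component 1 because of its interaction with component 3, and then rejects component 3, has the needed coefficient in hand. This has force and lowers the practical risk. It does not close the gap: Step 2's listed inputs concern feasibility and acceptability, and Step 3 is worded as automatic inclusion.

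A second reply is that the sequence is conditional. It needs a sizeable sympathetic interaction, little effect without the partner, both components passing Step 1, and a rejection at Step 2. That is correct. The documents offer no evidence of such an interaction and no rejection rate. With an interaction smaller than the main effect, the survivor keeps a positive predicted effect and Step 3 does no harm.

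Two stronger readings should be resisted. A reader might take the 72% as the rate at which the plan goes wrong; it is only the chance that component 1 passes Step 1 in a constructed scenario. A reader might also infer that the model will always predict nothing for the stranded component. In the illustration that prediction is zero or negative in about 61% of the trials in which both pass, and positive in the rest.

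**Conclusion.** The gap is real. The written rules allow a component to enter on the strength of a partner, allow the partner to be removed, and then include the survivor without a further look. The one interaction safeguard covers antagonism and comes before any removal.

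In the illustration, the pair is exposed to a Step 2 rejection in about 43%, 59% and 93% of trials for with-partner effects of 0.40, 0.50 and 0.80 SD, each to be multiplied by an unknown rejection probability. These figures rest on no effect at all without the partner, random attrition to n = 158, two-sided p < .10 and, for minutes, an SD of 77.5. They show that the route is open, not that it is likely to be taken.

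The documents do not support a claim that the final package will contain an inactive component, or that the Step 1 estimates or the power statement are wrong; those are unaffected. This is a cheap improvement to the decision rule.

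**What to change.** Add a short step between Steps 2 and 3 in section 9.6:

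1. In the fitted model, set each removed component to -1 and each retained one to +1.
2. Report each retained component's predicted effect at those settings, in min/week with a 90% CI.
3. Return to the meeting, without dropping it automatically, any component whose predicted effect is no longer positive.
4. For component 4, apply special case 1 at the final settings instead: it should raise attendance and not reduce minutes. A general requirement of a positive effect on minutes would contradict that rule, which accepts a zero effect on minutes.

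The cost is a few lines of text and one contrast per retained component, with no new data and no change to design or sample size.

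The downside is precision. The SE rises from 0.159 to about 0.225 SD with one partner fixed, and to √4 × 0.159 = 0.318 SD with all three partners fixed in a two-way model. The result should therefore inform the decision by sign and size and not serve as a new significance test. With only the removed partner fixed, it would flag about 61% of the affected trials at 0.50 SD. Fixing the other partners as well adds noise and would bring that share nearer to one half. The text should say that the check reduces the problem and does not eliminate it.

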10. DATA COLLECTION AND QUALITY ASSURANCE

10.1 Data Collection Forms

Most data will be collected and entered directly into REDCap. Data collected on paper CRF will be double-entered into REDCap. There will also be a database that we will use for tracking participants.

Any data, forms, reports, audio recordings, and other records that leave either recruitment site will be identified only by a participant identification number (Study ID, SID) to maintain confidentiality. All paper records will be kept in a locked file cabinet. All data collected will be entered into an electronic database which is stored on a secure server (REDCap) that is backed up on a daily basis. Participant identifying information will be stored in a separate REDCap database. Care New England's instance of REDCap has been deemed HIPAA compliant by CNE Information Technology.

10.2 Data Management

All data will be collected via REDCap. Paper CRFs, when collected, will be double-entered into REDCap. The Data Manager, [name] will oversee the REDCap database. Any discrepancies will be resolved by the Project Manager in consultation with the MPIs as needed.

Please see also “Data Handling and Record Keeping” in the DSMP.

10.3 Quality Assurance

10.3.1 Training

All research personnel, including yoga instructors will have formal training in research with human subjects (e.g., CITI training, NIH Human Subjects training). Drs. [name], [name], [name], [name], [name], and [name], and [name] will provide training to and supervise research assistants. Research assistants will also have training in Good Clinical Practice. Drs. [name] and [name] will provide training and supervision to yoga instructors.

10.3.2 Quality Control Committee

Drs. [name], [name], [name], [name], [name], and [name] will be responsible for quality control of this study. They review recruitment and retention reports, and AE reports, on weekly basis.

10.3.3 Metrics

Protocol Deviations

During weekly study meetings, protocol deviations will be discussed with the MPIs, including plans for corrective action. Drs. [name] or [name] (at CODAC) or [name] (at BMC) will also be alerted to deviations as they occur and will alert the MPIs for any deviation requiring immediate action. Protocol deviations will be logged on the protocol deviation tracking sheet and filed in the regulatory binder.

All assessment time points have a window of time for completion. However, typically due to circumstances outside of the control of the research staff, assessments occasionally occur outside of that window. Assessments that occur outside of the recommended window for completion will be considered to be protocol deviations, and will be logged as such.

Protocol deviations will be reported to NCCIH once per year, in the annual review. The SMC will also receive a list of protocol deviations in their interim or annual reports. Per Butler Hospital IRB policy, “major protocol deviations/violations, defined as those which increase risk to participants” will be reported promptly to the IRB and no more than 10 working days after the investigator is aware of the event. Minor protocol deviations do not need to be reported.

10.3.5 Monitoring

[name] or [name] will conduct protocol and data quality monitoring twice a year at each study site using the Quality Management review checklists. During Phase 1, all participant and other study records will be reviewed. During Phase 2, a random sample of 10-20% of participant and study records will be reviewed at each monitoring time point.

11. PARTICIPANT RIGHTS AND CONFIDENTIALITY

11.1 Institutional Review Board (IRB) Review

This protocol and the informed consent documents and any subsequent modifications will be reviewed and approved by the IRB or ethics committee responsible for oversight of the study. The consent form should be separate from the protocol document.

11.2 Informed Consent Forms

Informed consent will be obtained from each participant. The consent form will describe the purpose of the study, the procedures to be followed, and the risks and benefits of participation. A copy will be given to each participant and this fact will be documented in the participant's record.

11.3 Participant Confidentiality

Any data, forms, reports, audio recordings, and other records that leave the site will be identified only by a participant identification number (Study ID, SID) to maintain confidentiality. All paper records will be kept in a locked file cabinet. All data collected will be entered into an electronic database which is stored on a secure server (REDCap) that is backed up on a daily basis. Participant identifying information will be stored in a separate database and will be password protected and stored on a secure server. Care New England's instance of REDCap has been deemed HIPAA compliant by CNE Information Technology.

Information will not be released without written permission of the participant, except as necessary for monitoring by IRB, the FDA, the NCCIH, and the OHRP.

11.4 Study Discontinuation

The study may be discontinued at any time by the IRB, the NCCIH, the OHRP, or other government agencies as part of their duties to ensure that research participants are protected.

12. COMMITTEES

There will be a Safety Monitoring Committee.

13. PUBLICATION OF RESEARCH FINDINGS

Drs. [name] and [name] will be responsible for oversight and approval of any publications or presentations that arise from this research.

15. SUPPLEMENTS/APPENDICES

None
